1.2 DRUG PROFILE

BI 1265162 is a potent epithelial sodium channel (ENaC) inhibitor in phase 2 for the treatment of cystic fibrosis (CF) and chronic obstructive pulmonary disease (COPD).

[REDACTED]

[REDACTED]

[REDACTED]

1.2.2 Safety pharmacology

For a detailed description, refer to the current 'Investigator's Brochure', [c16304878](#).

1.2.3 Toxicology

For local tolerance, single and repeated inhaled dose toxicity, as well as genotoxicity studies, refer to the current 'Investigator's Brochure', [c16304878](#).

Oral toxicity studies

In the pivotal 7-day oral study in *rats*, nephropathy (bilateral, widespread tubular basophilia, interstitial mononuclear cell infiltration, tubular basement membrane thickening and glomerulosclerosis) was seen in 1 out of 10 female rats at the dose of 200 mg/kg/day. A BI 1265162-related effect could not be ruled out with certainty. The finding correlated with elevated kidney weight, higher blood urea and creatinine values, and protein in the urine in the affected animal only. Based on the equivocal finding in the kidney, the NOAEL was cautiously set at 100 mg/kg/day, corresponding to the C_{max} of 19.8 and 38.9 nM and AUC_{0-24h} of 65.9 and 118 nM*h for males and females, respectively [[n00264885](#)].

Oral administration of BI 1265162 to *dogs* caused death of one male dog after 8 days given 30 mg/kg in the DRF study [[n00260481](#)]. Substantial electrolyte changes and high systemic exposure with C_{max} values of 7480 and 3000 nM were seen on Days 1 and 8, respectively, in this animal. In the pivotal 7-day repeat dose study, plasma aldosterone at all doses and changes in urine electrolytes were observed at 10 mg/kg. The NOAEL was set at 10 mg/kg/day, corresponding to the C_{max} of 874 and 565 nM and AUC_{0-24h} of 2300 and 1320 nM*h for males or females, respectively [[n00261317](#)]. The NOEL level was set at 3 mg/kg, corresponding to the C_{max} of 283 and 146 nM and AUC_{0-24h} of 670 and 415 nM*h for males or females, respectively.

Intravenous toxicity studies

In the pivotal 7-day IV study in *rats*, the NOAEL was set at the highest dose of 1600 μ g/kg/day, corresponding to the C_{max} of 1360 nM and an AUC_{0-24h} of 616 nM*h (males & females combined) [[n00264887](#)].

An intravenous administration of BI 1265162 over 30 minutes to *dogs* was well tolerated up to 500 μ g/kg/day in the DRF and pivotal 7 day study [[n00260429](#), [n00260959](#)]. Pharmacodynamic related increases in plasma aldosterone were observed at 150 and 500 μ g/kg/day. The IV NOAEL was set at 500 μ g/kg/day, corresponding to the C_{max} of 2300 and 3520 nM and AUC_{0-24h} of 1600 and 2030 nM*h for males or females, respectively.

1.2.6 Residual Effect Period

The Residual Effect Period (REP) of BI 1265162 is 7 days. This is the period after the last dose with measurable drug levels and/ or pharmacodynamics effects is still likely to be present.

1.2.7 Drug product

BI 1265162 oral solution and concentrate for infusion

For this trial, an oral solution and a concentrate for infusion have been developed in addition to the inhalation formulation [REDACTED]

[REDACTED]. The concentrate for infusion contains 5 µg BI 1265162/ mL (0.36 MBq/ mg).

The oral solution contains 0.25 mg BI 1265162/ mL (0.06 MBq/ mg).

For shelf-life and storage conditions, refer to the instructions on the label.

For a more detailed description of the BI 1265162 profile, refer to the current 'Investigator's Brochure', [c16304878](#).

1.3 RATIONALE FOR PERFORMING THE TRIAL

Rationale for trial

The development of BI 1265162 was optimized for inhalation. However, as the application of inhaled radio-labelled substance is technically challenging, the intravenous application of BI 1265162 (C-14) will mimic the systemic exposure as if the compound was inhaled. The oral dose investigates the absorption and metabolism of the swallowed portion of the inhaled dose.

Therefore, this trial will be performed in 2 parts to characterize by means of mass balance

- (Part 1) basic pharmacokinetics, metabolism (metabolic profile) and routes of elimination of BI 1265162 (C-14) after intravenous administration, and
- (Part 2) the extent of gastrointestinal absorption, metabolism (metabolic profile), and routes of elimination of BI 1265162 (C-14) after oral administration.

The oral application of BI 1265162 (C-14) is intended to determine the extent of absorption of BI 1265162 and/ or its metabolites from the gastrointestinal tract. Due to the optimization of BI 1265162 for inhalation, this oral fraction is small (see also [Table 1.3: 1](#)). If metabolites will be formed in the gastro-intestinal tract and absorbed into the systemic circulation, their presence will be detected.

The data are required for future regulatory interactions, to further understand the pharmacokinetics of BI 1265162, including the quantitative determination of elimination pathways and drug metabolites.

Rationale for dose selection

The dose selection is based on previous experience with orally, inhaled and intravenously applied BI 265162 in healthy male subjects.

(i) Rationale for the intravenous dose

According to preliminary results of study 1399-0014, the single intravenous dose of 50 µg of BI 1265162 was well tolerated and safe. Comparing systemic exposures after the inhaled (trial 1399-0001, [Table 1.2.4: 1](#)) and intravenous (1399-0014, [Table 1.2.4: 2](#)) application of BI 1265162, mean C_{max} and AUC values after the intravenous application of 50 µg should correspond to those after the inhalation of 300 µg to 600 µg, and 600µg to 1200 µg, respectively. All doses were well tolerated and safe. The infusion time of 1 hour was chosen to limit the peak exposure and to better mimic the exposure after inhalation.

(ii) *Rationale for the oral dose*

According to preliminary results of study 1399-0014, the single oral dose of 1.25 mg of BI 1265162 seemed to be well tolerated and safe. The SAE was not assessed to be related to the oral application of BI 265162. Since the systemic exposure was lower than expected, the application of a 5 mg dose of BI 1265162 was chosen to achieve a meaningful systemic exposure in this study. For the pharmacokinetic rationale, see below.

However, an oral BI 1265162 dose of 5 mg has not been applied in humans before. A de-novo estimation of a safe starting dose was performed by applying the relevant algorisms of the FDA guidance ‘Estimating the Maximum Safe Starting Dose in Initial Clinical Trials for Therapeutics in Adult Healthy Volunteers’ [R06-1037] and the ICH guideline M3(R2) on ‘Non-clinical Safety Studies for the Conduct of Human Clinical Trials and Marketing Authorisation for Pharmaceuticals’ [R15-0594]. The results are displayed in [Table 1.3: 1](#) along with the relevant pharmacokinetics obtained from human studies.

Table 1.3: 1 Estimation of safe starting doses based on toxicological results in rats and dogs exposed to BI 1265162

	Human	Dog	Rat
FDA Approach			
NOAEL [mg/kg]		10	100
NOEL[mg/kg]		3	
Conversion Factor		1.8	6.2
HED for 60 kg Human (NOAEL) [mg]		333	967
HED for 60 kg Human (NOEL) [mg]		99.6	
Safety Factor of 10 on HED (NOAEL) [mg]		33.3	96.7
Safety Factor of 10 on HED (NOEL) [mg]		9.96	
ICH M3(R2) Approach			
HED for 60 kg Human (NOAEL) [mg]		333	967
C_{max} at NOAEL [pmol/L] at Day 1		M: 927,000; F: 458,000	
AUC at NOAEL [pmol·h/L] at Day 1		M: 2,620,000; F: 1,300,000	
HED for 60 kg Human (NOEL)		99.6 mg	
C_{max} at NOEL [pmol/L] at Day 1		M: 228,000; F: 234,000	
AUC at NOEL [pmol·h/L] at Day 1		M: 655,000; F: 544,000	
Safety Factor of 50 on C_{max} (NOEL) [pmol/L]		M: 4,560; F: 4,680	
Safety Factor of 50 on AUC (NOEL) [pmol·h/L]		M: 13,100; F: 10,800	
Human pharmacokinetic parameters (gMean (gCV) after single doses of BI 1265162			
1399-0001			
C_{max} after 1200 µg inhaled [pmol/L]		6500 (73.1)	
AUC after 1200 µg inhaled [pmol·h/L]		3920 (76.4)	
1399-0014 (ongoing)*			
1.25 mg PO (N=4)			
C_{max} [pmol/L]		57.7 (69.0)	
$AUC_{0-\infty}$ [pmol·h/L]		316 (83.5)	
50 µg IV (N=4)			
C_{max} [pmol/L]		1880 (8.79)	
$AUC_{0-\infty}$ [pmol·h/L]		2200 (12.2)	
Absolute bioavailability[%]		0.6	

* Preliminary, not validated data; subject to change!

Proprietary confidential information © 2020 Boehringer Ingelheim International GmbH or one or more of its affiliated companies

According to the FDA algorithm, the dog is the most sensitive species after the oral application of BI 1265162. the dog NOEL is based on urine electrolyte changes . Using a standard safety factor of 10 resulted in a maximum safe ORAL starting dose of 9.96 mg which is above the oral dose of 5 mg planned in this study.

The systemic exposures in female dogs at the HED of NOEL is 234,000 pmol/L for C_{max} at Day 1 and 544,000 pmol*h/L for AUC. The application of a safety factor of 50, as recommended by the ICH M3(R2) guideline, results in systemic exposures of 4,680 pmol/L for C_{max} and 10,800 pmol*h/L for AUC. These are well above the expected exposure to be seen with 5 mg oral dosing as referenced to the values obtained already with 1.25 mg oral administration in man.

Even though the intended oral application of 5 mg is 4-times higher than that applied in trial 1399-0014, the expected corresponding systemic exposures should be below those seen after 1200 μ g inhaled and 50 μ g IV as achieved safely in studies 1399-0001 and 1399-0014, respectively.

Rationale for trial population

The inclusion of male healthy subjects as a trial population in phase I studies is ideal as they provide relatively stable physiological, biochemical and hormonal conditions for studying drug effects. Healthy subjects can be tested under standardised conditions in an environment which allows repeated testing.

1.4 BENEFIT - RISK ASSESSMENT

Participation in this trial is without any (therapeutic) benefit for healthy subjects. Their participation in the trial, however, is of major importance to the development of BI 1265162. Subjects are exposed to the risks of the trial procedures and the risks related to the exposure to the trial medication.

Procedure-related risks

The use of an indwelling venous catheter or venepuncture for e.g. blood sampling may cause a syncope or result in mild bruising, and in rare cases, in transient inflammation of the wall of the vein, or nerve injury, potentially resulting in paraesthesia, reduced sensibility, and/or pain for an indefinite period. The same risks apply to venepuncture for blood sampling.

The solvent for the intravenous infusion containing a mixture of labelled and unlabelled BI 1265162 is isotonic sodium chloride solution (0.9%) adjusted to pH 4.0. Therefore, in case of inadvertent paravenous drug administration apart from local swelling, no tissue damage is expected.

The total volume of blood withdrawn per subject during the entire trial will not exceed the volume of a normal blood donation (500 mL). No health-related risk to healthy subjects is expected from withdrawal of this volume of blood.

Drug-related risks and safety measures

BI 1265162

As the nature of the target and the mechanism of action of BI 1265162 are well understood, comparable compounds have been tested internally and by other companies before, and the animal models are believed to be predictive for the effects in humans, BI 1265162 is not seen as a high risk compound. The specific mechanism of action is also well recognized for when administered systemically (orally) as a diuretic with a well-established safety profile.

The pharmacological effects of BI 1265162 seem to be dose dependent and no evidence for prolonged or irreversible effects has been observed. Both formulations, oral as well as intravenous, were used in the absolute bioavailability study 1399-0014. However, a 4-times higher oral dose of 5 mg is intended to be applied to ensure a meaningful exposure to the study drug.

A clinically relevant hyperkalaemia after the administration of a single dose of BI 1265162 is unlikely. However, safety laboratory will be performed with special focus on serum electrolytes (see [Flow Chart](#)).

BI 1265162 (C-14)

(Part 1) No therapeutic intravenous use is planned for BI 1265162. Therefore, in accordance with the guideline on non-clinical safety studies ICH-M3(R2) [[R15-0594](#)], the intravenous dose of 50 µg BI 1265162 (C-14) is considered adequately qualified by the existing oral toxicity studies. The investigation of intravenous local tolerance of drug substance is not recommended in this situation because the administered dose is very low (< 100 µg) and no novel solvent is used. BI 1265162 is labelled with the isotope (C-14) which is necessary for the purposes of this trial to identify the metabolism (metabolic profile) and routes of elimination BI 1265162.

(Part 2) BI 1265162 (C-14) is labelled with the isotope (C-14) which is necessary for the purposes of this mass balance trial. Therefore, subjects will be exposed to ionizing radiation. The effective dose that each subject receives from IV administration of 0.018 MBq is about 0.001 mSv. The effective dose that each subject receives from ORAL administration of 0.306 MBq is about 0.001 mSv.

Risk minimization

To mitigate the BI 1265162-related risks, the following safety measures will be applied in this trial with healthy subjects:

- Careful dose selection (see [Section 1.3](#)) for the different formulations
- Prior to starting the IV administration of trial medication there will be a function control of the venous access to prevent para-venous administration

Proprietary confidential information © 2020 Boehringer Ingelheim International GmbH or one or more of its affiliated companies

- The IV administration will be performed as a slow infusion over 1 hour to ensure slowly rising plasma concentrations
- Hyperkalaemia after the application of a single dose of BI 1265162 seems to be unlikely. However, due to the mode of action of this compound, frequent examinations of serum potassium will be performed (see [Flow Chart](#))
- Subjects with impaired kidney function will be excluded from the trial
- Subjects will stay at the trial site from the day prior each dosing until at least 8 days after the administration of the trial drug

Although rare, a potential for drug-induced liver injury (DILI) is under constant surveillance by sponsors and regulators. Therefore, this trial requires timely detection, evaluation, and follow-up of laboratory alterations in selected liver laboratory parameters to ensure subjects' safety (see [Section 5.2.6.1.4](#), adverse events of special interest).

To mitigate the radio-burden related risks, the following safety measures will be applied in this trial with healthy subjects:

- Each subject participates either in Part 1 or in Part 2 but not in both parts.
- (Part 1) The radioactive dose per infusion will be about 0.018 MBq giving a burden of 0.001 mSv and thereby falls into the ICRP 1 category (trivial level of risk) based on the calculated ICRP Category I limit for administration of (C-14) BI 1265162 of 1.8 MBq [[c25192159](#), [R15-3219](#)].
- (Part 2) The orally applied radioactive dose is 0.306 MBq which is expected to give a radiation burden of 0.0014 mSv. This is lower than the limit proposed by ICRP Category 1, (<0.1 mSv – risk defined as trivial). For details on the radiation burden calculation, see [Appendix 10.1](#). For clinical investigations to study the disposition, metabolism and excretion of new pharmaceutical compounds in man an effective dose of below 0.1 mSv is considered to be trivial [[R15-3219](#)].

2. TRIAL OBJECTIVES AND ENDPOINTS

2.1 MAIN OBJECTIVES, PRIMARY AND SECONDARY ENDPOINTS

2.1.1 Main objectives

The main objectives of this trial is to investigate (a) rates and routes of excretion, (b) mass balance, (c) pharmacokinetics of parent drug, any known metabolites, and total radioactivity, (d) metabolite profiling, metabolite identification, if suitable assays are available, (e) safety and tolerability in healthy male subjects.

2.1.2 Primary endpoints

The following parameters will be determined:

(Part 1 & 2) Mass balance recovery of total (C-14) BI 1265162-radioactivity in urine and faeces (and vomit, if applicable). Amount of radioactivity excreted as a percentage of the administered single intravenous or oral dose of BI 1265162 (C-14) in

- Urine - $fe_{urine, 0-t2}$ (fraction of (C-14)-radioactivity excreted in urine as percentage of the administered dose over the time interval from 0 to the last quantifiable time point)
- Faeces - $fe_{faeces, 0-t2}$ (fraction of (C-14)-radioactivity excreted in feaces as percentage of the administered dose over the time interval from 0 to the last quantifiable time point)
- Vomit - $fe_{vomit, 0-t2}$ (fraction of (C-14)-radioactivity excreted in vomit as percentage of the administered oral dose over the time interval from 0 to the last quantifiable time point) - if feasible and appropriate

The timeframe for determination of these endpoints depends on the time of discharge of each subject, based on radioactivity excretion, and is predicted to vary between 9 and 38 days after drug administration.

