	36	840:00	08:00	Admission to trial site ^{11,12}			▲	+	+					
	37	864:00	08:00	Discharge from trial site ¹¹	B					x	x		▼	
3	9 to 38			End-of-trial (EoT) examination ^{10,13}	A ¹⁸					x	x			

Proprietary confidential information © 2020 Boehringer Ingelheim International GmbH or one or more of its affiliated companies

A & B: Safety laboratory sets (see [Table 5.2.3: 1](#))

1. Subject must be informed and written informed consent obtained prior to starting any screening procedures. Screening procedures include physical examination, check of vital signs, ECG, safety laboratory (including drug screening), demographics (including determination of body height and weight, smoking status and alcohol history), relevant medical history, concomitant therapy and review of inclusion/ exclusion criteria.
2. Pharmacokinetics (PK): BI 1265162 and its metabolite(s) in plasma (see [Section 5.3.2.3](#)); (C-14) BI 1265162 - radioactivity in whole blood and plasma (see [Section 5.3.2.2](#)). Blood sampling for an individual subject can be stopped, if (C-14) BI 1265162 -radioactivity in plasma is below limit of detection (< LLOQ 10 dpm/ mL) at two consecutive sampling time points for this subject (earliest stopping after Day 9).
3. The time is approximate; the respective procedure is to be performed and completed within 3 hours prior to drug administration.
4. If several actions are indicated at the same time point, the intake of meals will be the last action.
5. Safety laboratory including urine drug and alcohol screening.
6. Urine collection intervals (for PK/(C-14) BI 1265162 -radioactivity assessment and metabolic profiling; planned time): on Day -1 or Day 1 pre-dose (blank) sample, on Day 1 prior to start of urine collection voiding of the bladder, 0-4 , 4-8, 8-12, 12-24, 24-48, 48-72, 72-96, 96-120, 120-144, 144-168, and 168-192 hours after administration of BI 1265162 (C-14). Thereafter 24-h collections are to be performed on Days 15-16, 22-23, 29-30, and 36-37. Urine sampling for PK/ (C-14) BI 1265162 -radioactivity will be stopped when release criteria for radioactivity recovery (see [Section 3.1](#)) have been met (earliest stopping on Day 9). “+” means end of last collection interval, start of following collection interval. For details on sample usage, see [Section 5.3.2.5](#).

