2.2.2 Further endpoints

2.2.2.1 Further pharmacokinetic endpoints

The following pharmacokinetic endpoints after a single intravenous and oral dose of BI 1265162 (C-14) will be calculated for total (C-14) BI 265162-radioactivity, BI 1265162 and its metabolite(s) in whole blood, plasma, urine and faeces (as feasible and appropriate), and may include

- $AUC_{t_1-t_2}$ (Area under the concentration-time curve of the analyte in plasma over the time interval from time point t_1 to t_2)
- $AUC_{0-\infty}$ (Area under the concentration-time curve of the analyte over the time interval from 0 extrapolated to infinity)
- $\%AUC_{t_2-\infty}$ (the percentage of $AUC_{0-\infty}$ obtained by extrapolation)
- t_{max} (time from dosing to maximum measured concentration of the analyte)
- λ_z (terminal rate constant)
- $t_{1/2}$ (terminal half-life of the analyte)
- MRT_{po} (mean residence time of the analyte in the body after oral administration)
- MRT_{iv} (mean residence time of the analyte in the body after IV administration)
- CL/F (apparent clearance of the analyte in the plasma after extravascular administration)
- CL (apparent clearance of the analyte in the plasma after intravascular administration)
- V_z/F (apparent volume of distribution during the terminal phase after extravascular administration)
- Ae_{urine, t_1-t_2} (amount of analyte that is eliminated in urine from the time interval t_1 to t_2)

Proprietary confidential information © 2020 Boehringer Ingelheim International GmbH or one or more of its affiliated companies

- $Ae_{urine, 0-t2}$ (amount of analyte that is eliminated in urine over the time interval from 0 to the last quantifiable time point)
- $fe_{urine, t1-t2}$ (fraction of administered drug excreted in urine from time point t1 to t2)
- $Ae_{faeces, t1-t2}$ (amount of analyte that is eliminated in faeces from the time interval t1 to t2)
- $Ae_{faeces, 0-t2}$ (amount of analyte that is eliminated in faeces over the time interval from 0 to the last quantifiable time point)
- $fe_{faeces, t1-t2}$ (fraction of administered drug excreted in faeces from time point t1 to t2)
- $CLR, t1-t2$ (renal clearance of the analyte in plasma from the time point t1 to t2)

Further pharmacokinetic parameters may be calculated as appropriate.

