3. DESCRIPTION OF DESIGN AND TRIAL POPULATION

3.1 OVERALL TRIAL DESIGN AND PLAN

The overall trial design is depicted in [Figure 3.1: 1](#) and [Figure 3.1: 2](#).

The trial will consist of two trial parts, after the BI 1265162 (C-14) administration of single (Part 1) intravenous and (Part 2) oral doses. Both parts will be performed as a non-randomized, open-label, single-dose, single arm, trial in healthy male subjects in order to investigate by means of mass balance recovery (Part 1) metabolism (metabolic profile) and routes of elimination of (C-14) BI 1265162 after intravenous administration of 50 µg BI 1265162 (C-14) and (Part 2) the extent of oral absorption, metabolism (metabolic profile),

Proprietary confidential information © 2020 Boehringer Ingelheim International GmbH or one or more of its affiliated companies

and routes of elimination of (C-14) BI 1265162 after oral administration of 5 mg BI 1265162 (C-14). For details, see [Section 4.1](#).

Since in both parts different subjects will take part, there will be no washout period.

On Day 1, subjects will receive the (C-14)-labelled drug substance and will then stay in the trial centre up to the morning of Day 9 for collection of blood, urine, and faeces samples. Subjects will be readmitted to the trial centre for 24 hour collection intervals of urine and faeces on Days 15, 22, 29, and 36, if release criteria as specified below have not been met on Day 9 or during any subsequent 24-h collection visits. Within 24 hours before each of these once-weekly in-house collection intervals, subjects are to collect faeces at home. This 24 hour interval home collection faeces will be used for analysis in case no defecation occurs in the subsequent 24 hours in-house collection interval. Otherwise it will be discarded.

For determination of whether release criteria have been reached for individual subjects, (C-14)-radioactivity will be measured in excreta (urine and faeces) as well as in plasma. The actual recovery results will be reported as a percentage of the administered dose.

If one of the following release criteria is true, 24 hour collection intervals after Days 9, 16, 23, 30, or 37, (whichever is applicable) will not be performed:

- Greater than or equal to 90% of the administered dose has been recovered in urine and faeces combined over the investigational period, or
- If <1% of the dose administered has been collected in urine and faeces within 2 separate, consecutive 24 hour intervals, and

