17. Blood donation of more than 100 mL within 30 days of planned administration of trial medication or intended blood donation during the trial
18. Intention to perform excessive physical activities within 96 hours prior to the administration of trial medication and during the trial until the discharge at Day 9
19. Inability to comply with the dietary regimen of the trial site
20. A marked baseline prolongation of QT/QTc interval (such as QTc intervals that are repeatedly greater than 450 ms) or any other relevant ECG finding at screening
21. A history of additional risk factors for *Torsade de Pointes* (such as heart failure, hypokalaemia, or family history of Long QT Syndrome)
22. Subject is assessed as unsuitable for inclusion by the investigator, for instance, because the subject is not considered able to understand and comply with trial requirements, or has a condition that would not allow safe participation in the trial

In addition, the following trial-specific exclusion criteria apply:

23. A history of chronic kidney disease
24. Participation in another ADME study with a radiation burden of 0.1-1.0 mSv in the period of 1 year prior to screening or 1.1-2.0 mSv in the past 2 years or 2.1-3.0 mSv in the past 3 years etc.
25. Exposure to radiation for diagnostic reasons (except dental X-rays and plain X-rays of thorax and bony skeleton (excluding spinal column) in the period of 1 year prior to screening)
26. Irregular defecation pattern (less than a mean of one bowel movement every other day)

For trial restrictions, see [Section 4.2.2](#).

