5.3.2.6 Faeces sampling

Faeces will be collected during the trial as indicated in the [Flow Chart](#).

A blank faeces sample will be collected prior to drug administration.

All stool samples will be collected quantitatively in portions up to Day 37 after drug administration. The weight of faeces and the exact times of faeces collection will be recorded in the eCRF.

All faeces samples are planned to be used for determination of (C-14)-radioactivity and metabolic profiling.

[figure not shown]
[figure not shown]
Samples to be used for metabolic profiling will be selected according to the levels of radioactivity in each faeces sample interval.

For a detailed description of faeces sampling, sample volume, sample handling, sample preparation, sample storage, tube labelling and sample shipment, refer to the laboratory manual.

[figure not shown]

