- Using the data of the BI 1265162 study in rats after intravenous and intratracheal administration a half-life of total ¹⁴C-activity of 30 hours is estimated, with a half-life of the parent compound of 7.4 hours; in humans a terminal phase half-life of BI 1265162 of approximately 15.5 hours is assumed⁵. In the current estimation a half-life of total BI 1265162-derived radioactivity of $15.5 / 7.4 \times 30 = 63$ hours is used.
- The absorbed fraction is 1, as it is administered intravenously.
- Based on the excretion study in rats ¹⁴C-radiolabeled BI 1265162 is found to be excreted both in feces and in urine. For the calculation is assumed: 85% of the intravenously administered radioactivity is excreted via the gastrointestinal tract in feces and 15% is excreted via the kidneys.

Based on these assumptions the estimated effective radiation burden after a single intravenous radioactivity dose of ¹⁴C-radiolabeled BI 1265162 is approximately 0.05 mSv/MBq.

As the radiolabeled dose which can be given intravenously is limited by the pharmacological dose (maximum dose planned 200 µg) and the specific activity (approximately 2.8 MBq/mg) the maximum possible label dose to be given intravenously in this study is 0.56 MBq. The estimated effective radiation burden of this dose is 0.028 mSv.

For biomedical investigations in small groups of human volunteers an effective dose below 0.1 mSv is considered to be trivial⁶.

Proprietary confidential information © 2020 Boehringer Ingelheim International GmbH or one or more of its affiliated companies

Radiation Burden Calculation Report
BI 1399-0013; intravenous and oral dosing
Version Date: 20JUN2019

Appendix A1: Radiation burden of the gastrointestinal tract after intravenous administration of 1.0 MBq ^{14}C BI 1265162

Using SEE-values, an organ-specific radiation burden can be estimated. The SEE-value is dependent, among other factors, on the mass of the target organ and the type of radiation.

With these SEE-values and the number of disintegrations U in the target organ, the organ dose equivalent H_t is calculated:

$H_t = \text{constant} \times U \times \text{SEE}$ (mSv); using a target organ-related weight factor, the contribution of the organ burden to the body burden is translated as: $H_{wb,t} = H_t \times \text{weight factor}$ (mSv)

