In order to be able to calculate the radiation burden of the GI tract, this has been divided in five sections, i.e., the stomach (st), the small intestines (si), the right part of the large intestines, the left part of the large intestines (lc) and the rectum / sigmoid (rs).

The SEE-values for these organs are:

ST:	1.0×10^{-5}	(weight factor = 0.12)
SI:	3.2×10^{-7}	(weight factor = 0.01)
RC:	2.3×10^{-10}	(weight factor = 0.048)
LC:	2.9×10^{-10}	(weight factor = 0.045)
RS:	9.2×10^{-10}	(weight factor = 0.027)

The number of disintegrations U in each target organ depends on the amount of radioactivity excreted, or any metabolites that are eliminated via the gall bladder that is standardised for the various compartments of the GI tract (constant). IO intravenous = 1.0 MBq; Excretion via GI tract: 85% of the dose, excretion via urine: 15% of the dose. These assumptions give:

H_{st} , H_{si} , H_{rc} , H_{lc} and H_{rs} are all 0.000 mSv.

total GI: = 0.0000 mSv

The total contribution of the GI tract to the effective dose (body radiation burden) amounts to 0.000 mSv.

Appendix A2: Radiation burden of the central compartment after intravenous administration of 1.0 MBq ^{14}C BI 1265162

Average body weight = 70 kg; SEE = 7.1905×10^{-7} ; 100% of the dose administered intravenously and excreted with a half-life of 63 hours. Total number of disintegrations in the central compartment after intravenous dosing is 268×10^9 with a tissue weighting factor of 0.95 (1 minus the weighting factors for the liver and uveal tract) giving a H_{wb} of 0.0285 mSv.

Appendix A3: Radiation burden of the uveal tract and the liver after intravenous administration of 1.0 MBq ^{14}C BI 1265162

For the liver SEE = 2.72×10^{-5} ; 17.2% of the dose administered iv excreted from the liver with a half-life of 9 hours with a weighting factor of 0.04 giving a contribution to the radiation burden of 0.0014 mSv.

For the uveal tract SEE = 0.884477 ; 0.004% of the dose administered iv excreted from this tissue with a half-life of 840 hours with a weighting factor of 0.01 giving a contribution to the radiation burden of 0.0245 mSv.

The contribution to the radiation burden for these two organs/tissues is 0.0259 mSv

The total effective dose (radiation burden), based on the above-mentioned worst case scenario for intravenous administration of 1.0 MBq ^{14}C -labeled BI 1265162 amounts to $0.0285 + 0.0259 = 0.05$ mSv.

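### Does the primary excretion fraction need a fixed 0–192 h window because collection after Day 9 has gaps?

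*Protocol*

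**What the plan says.** The primary endpoints in Protocol Section 2.1.2 (repeated in SAP Section 5.1) are the fractions of radioactivity in urine and faeces "as percentage of the administered dose over the time interval from 0 to the last quantifiable time point". The timeframe follows each subject's discharge and is expected to lie between 9 and 38 days.

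Flow Chart 1 has continuous collection from 0 to 192 h. For urine, footnote 6 continues: "Thereafter 24-h collections are to be performed on Days 15-16, 22-23, 29-30, and 36-37". Faeces are also collected at home for 24 h before each weekly stay, but that sample is discarded if a stool is passed in house. Section 3.1 drops the later collections "If one of the following release criteria is true": at least 90% of the dose recovered, or less than 1% in each of two consecutive 24-hour intervals together with plasma radioactivity below 5% of its maximum (my reading of how the three conditions combine).

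Section 2.2.2.1 lists interval fractions as further endpoints, for example the "fraction of administered drug excreted in urine from time point t1 to t2", and Section 2.2.2.2 lists cumulative recovery. Missing pharmacokinetic data are referred to a corporate procedure (Protocol Section 7.5.2) and to sponsor manuals (SAP Section 6.6).

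The SAP was written after the trial had stopped. Section 4 limits the analysis to Part 1. Section 6.1 calls Day 9 the earliest possible discharge and reports that all subjects were discharged then.

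**The concern.** For a recalled subject the last quantifiable time point moves to Day 16 or later. The endpoint then carries the label of a continuous interval but is a sum over separate windows. Uncollected excretion counts as zero, so the value is too low, and a low value could mean retention or merely days without collection. Averaging recalled subjects with those released on Day 9 would mix different windows. Recovery is the only primary endpoint and there are seven subjects, so one low value shows in the mean.

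Two further points add to the unease. The SAP still carries the 9-to-38-day timeframe (Section 5.1) and the time windows for collections after Day 9 (Section 6.7), as if recalls might be in the data. And Protocol Section 5.3.2.6 says "All stool samples will be collected quantitatively in portions up to Day 37 after drug administration", which does not match a weekly schedule.

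**Working it through.** **Length of the gaps** (Flow Chart 1 times). Urine is collected at 336–360, 504–528, 672–696 and 840–864 h. The first gap is 336 − 192 = 144 h, or 6 days, and the later ones are equal. Of the 864 − 192 = 672 h after Day 9, 4 × 24 = 96 h are collected (14.3%). For faeces, home collection starts at 312 h, so the first gap is 312 − 192 = 120 h (5 days) if the home sample is used, and 6 days if it is discarded.

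**The plan's own half-life.** Appendix 10.1 scales the rat value: 15.5 / 7.4 × 30 = 62.8, stated as 63 h. It then takes the dose as "excreted with a half-life of 63 hours". The figure is reproduced. The report presents its assumptions as a worst case.

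**Size if all excretion runs at 63 h.** Assume mono-exponential excretion, with r(t) = 2^(−t/63) still to be excreted and everything eventually recovered.
- By 192 h: 1 − r(192) = 87.91%. The last two days give 4.76% and 3.65%, so there is no release on Day 9.
- Uncollected in 192–336 h: 9.61%.
- Collected in 336–360 h: 0.576%; in 504–528 h: 0.091%. Both are below 1%, so release comes on Day 23 if plasma permits.
- Collected by 528 h: 87.91 + 0.576 + 0.091 = 88.57 (rounded components), against 1 − r(528) = 99.70% excreted. Gap: 11.13 points.
- Effect of one such subject on a mean of seven: 11.13 / 7 = 1.59 points.

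**How far this depends on the half-life.** At 15.5 h, the human parent value in Protocol Section 3.2, only 0.02 points remain at 192 h and there is no recall. Under full recovery, recall needs a half-life above 192 × ln 2 / ln 10 = 57.8 h. If only 95% is ever recovered the threshold is 45.2 h; at 90% it is 26.8 h.

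**If only a slow phase runs at 63 h.** Section 3.2 calls elimination multi-exponential. Let a share p of the dose be in the slow phase and the rest be out by 192 h. With r(192) = 12.09%, missing 90% on Day 9 requires:
- full recovery: p × 12.09 > 10, so p above about 83%;
- 95% recovery: p × 12.09 > 5, so p above about 41%;
- 90% recovery: the 1% limb decides, p × 4.76 ≥ 1, so p of about 21%.

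**Part 2.** With 7.6% absorbed (Appendix 10.1) and the rest out by 192 h, recovery at 63 h is 92.4 + 7.6 × 0.8791 = 99.1%, so release on Day 9. Part 2 was not run.

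**Was anyone recalled?** Flow Chart 1 sends every subject home on Day 9, recalled or not. Calling Day 9 the earliest discharge, as SAP Section 6.1 does, is informative only if discharge means final release. Protocol Section 2.1.2 uses the word that way when it makes the timeframe depend on discharge according to excretion. On that reading all seven subjects share a window of about 0–192 h and the gap is zero.

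**Would the obvious remedies help a recalled subject?** A primary endpoint cut at 192 h reports 87.9% where the planned sum reports 88.6%; excretion is 99.7%. It gives a common window but moves further from the truth. Filling the gaps from urine needs a constant faeces-to-urine ratio, which the documents do not support. In a simulated case with a urinary half-life of 45 h and a faecal one of 63 h, 88.7% was measured, 93.3% was obtained after filling and 99.7% was excreted. With a stool on 50% of days, which is the limit set by exclusion criterion 26 ("less than a mean of one bowel movement every other day"), the filled total had an error SD of 9.8 points.

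**The case for a change.** The strongest reply is that SAP Section 6.1 does not settle the matter. Flow Chart 1 has further discharges after each readmission, and its footnote 10 speaks of a last discharge, so a Day 9 discharge could be only the scheduled one. The radiation report also assumes that "85% of the intravenously administered radioactivity is excreted via the gastrointestinal tract in feces and 15% is excreted via the kidneys", so most of the dose leaves by the route where stool timing matters. With recovery as the sole primary endpoint, an SAP written after Part 1 could have said outright that no excreta were collected after 192 h.

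That last point stands: readmission is not excluded in so many words. The other signs of doubt are weak. SAP Section 5.1 is quoted protocol text, and Section 6.7 attributes its windows to the protocol's flow chart. The SAP also still refers to both parts although one never ran, so text carried over from the protocol says little about what happened.

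Nor can a missing rule be proved. The cited procedures are not available, and parts of the SAP are redacted or not shown, including a figure in Section 7.4.1. A reader who did meet a recalled subject would have the interval and cumulative recoveries, which show where collection stopped and whether excretion was still going on.

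**Conclusion.** The structural observation is right: a recalled subject's fraction omits six days of urine, and five to six days of faeces, between weekly visits. It does not call for a change. On the likely reading of SAP Section 6.1 nobody was recalled, and the effect on the seven analysed subjects is zero. The 11.1-point gap, or 1.6 points on the mean for one such subject, needs both a recall and a rat-scaled worst-case half-life applied to the whole dose; at the human parent half-life it is 0.02 points. The analysis is descriptive, with no hypothesis or decision threshold.

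If a recall did occur, a 192 h cut-off would discard measured recovery without correcting the understatement, and the gap-fill rests on a ratio that statisticians could fairly dispute. Interval and cumulative recovery are already listed, so recovery to 192 h can be shown without redefining the primary endpoint. The Day 37 wording in Protocol Section 5.3.2.6 is a clerical slip: the section itself opens by deferring to the Flow Chart.

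This conclusion rests on reading the Day 9 discharge as final release, which the SAP implies but does not state. A sentence saying so would be a courtesy to the reader; it would not alter the analysis.
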